We are currently conducting 'think-aloud interviews' with PPIE members to obtain immediate reactions to all elements and materials of the study. We are using purposive sampling to ensure we interview young people from different cultural, ethnic and socio-economic groups focussing on economically disadvantaged young people (who are at increased risk of developing mental health problems). Although analyses is ongoing, we analyse, tabulate, and discuss potential changes with the co-production team until there are no further changes required. We aim to maximise accessibility, usability, and credibility of our materials via our co-production team throughout the present study.

3. Aims & Objectives

Overall aim: To develop, optimise and evaluate a novel, accessible, engaging public health intervention.

The following research questions are designed to enable us to achieve our aim:

- 1. What are the most acceptable, and engaging co-produced brief smart-phone-delivered interventions for insomnia and mental health symptoms for young people aged 14-18 (especially those from economically disadvantaged backgrounds)?
- 2. How should we adapt SHUTi (which works for adults), for young people so it is engaging for those with acute (6 weeks) insomnia symptoms?
- 3. Are automated mental health interventions that have been shown to work for young people presenting to mental health services, acceptable for this group of young people?
- 4. How effective is the detection of early mental health symptoms using insomnia symptoms?
- 5. Do mental health symptoms reduce following a) STEP 1 online advice on improving sleep hygiene and b) STEP 2 adapted modular SHUTi insomnia programme?
- 6. How do young people experience the technology?
- 7. What is the most effective method to communicate with young people and our stakeholders to ensure rapid dissemination and widespread national take up?

4. Methodology

Overarching Design

A stepped care approach improves access to appropriate care. We propose the following staged approach:

- STEP 1: Online advice on improving sleep hygiene provided as automated accessible audiovisual materials suitable for economically disadvantaged young people and those from different cultural backgrounds.
- STEP 2: If symptoms persist, participants will be offered adolescent SHUTi (automated iCBT for insomnia) delivered in 6 modules.

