- STEP 3: If participants are seeking further advice for their mental health, they will be signposted to *Bite Back* (a web-based well-being programme).

Optimisation and Evaluation

An observational cohort with integrated qualitative methodology will provide the infrastructure to develop the web-based applications, test the feasibility and acceptability of passive data collection, online screening and data linkage. Follow up questions on insomnia, anxiety and depression symptoms at 6-weeks, 6- and 12-months will enable us to test detection efficacy. We will synthesise quantitative and qualitative data to explore the acceptability and feasibility of recruitment, the web-based applications, data collected, and retention.

Recruitment:

Participants (aged 14-18) will be recruited through our established collaborations with:

- The Association of Colleges (https://www.aoc.co.uk) (93% of all further education and 6th form colleges).
- E-Act Multi-academy trust (https://www.e-act.org.uk/) who have links with academies throughout the UK.

Recruitment will focus on schools and colleges from across the UK, with the aim to ensure participation of CYP from diverse and disadvantaged backgrounds. A poster describing the study will be shared within each school/college to encourage young people to participate. By scanning a QR code, participants will be directed to the participant information sheet on their smartphones. If the poster is shared electronically, participants will be asked to type the relevant URL into their mobile browser or text the study mobile number (via Twilio) which will send an automated reply with a link to the online participant information sheet.

All participants will receive two £10 vouchers as a thank you for their time. One after their baseline survey, and another after their 6-week (second) survey. If a participant decides to participate in a one-to-one interview, they will be rewarded with a £40 voucher.

Sample size:

A sample size of 1000 is a pragmatic choice as an achievable recruitment target and sufficient to answer research questions. If we assume 20% attrition, recruiting 1000 young people will provide data

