on 800, of which 240 (30%) will have insomnia symptoms at enrolment and 180 (75%) will also have mental health symptoms. Of those with healthy sleep, if the incidence of acute insomnia (one month or less) is similar to adults then 150 -210 (27-37%) will develop insomnia each year (of which 72% will recover). A cohort of this size will put confidence intervals around these assumptions.

Inclusion and Exclusion Criteria

Included: Young people:

- Aged 14-18,
- Who attend secondary school or college,
- Who have a mobile phone.

Excluded: Young people:

- Aged 14 or 15 who do not have the consent of their parent / carer,
- Who are receiving treatment for their insomnia and/or mental health difficulties.

Consent

All assent and consent data will be collected via Research Electronic Data Capture (REDCap) — a web-based data capture system for research. Assent will be collected from 14 and 15-year-olds. Consent from their parent/carer will be collected also. The REDCap form will prevent young people under the age of 16-years from continuing if parent/carer consent has not been obtained. Consent will be collected from 16-18-year-olds. An electronic signature will be requested from all individuals to ensure we are collecting verified consent. To participate in an interview and/or provide data linkage will be optional. Upon turning 16 years old, participants will be re-approached and re-consented.

Materials:

All participants will receive STEP 1 (Sleep Solved) throughout their participation. Phone Downtime app infers sleep disturbance through movement and screen on/off events on phones using the Android operating system. Only users with an Android phone will be offered to use this app. If high levels of sleep disturbance persist at and beyond 6-weeks, the participant will be signposted to STEP 2 (adapted SHUTi programme). STEP 2 will include approximately 6 modules (in-depth advice) on sleep hygiene and mental health. Notably, Sleep Solved will be available to all participants throughout their participation. Some participants will also be signposted to STEP 3 (*Bite Back*).

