The Phone Downtime app will only be offered to Android users and will undergo further optimisation throughout the study. The *Phone Downtime* app runs on phones using the Android operating system, and sleep disturbance is based on screen on/off events and an accelerometer to measure the movement. In this study, we aim to improve the software engineering to make it more extensible and flexible; investigate the trade-offs between the computational demands (data/memory), battery of additional modalities and potentially improved accuracy. In other words, we aim to minimise battery usage. The target sample size is significantly larger than the pilot studies that have been conducted with the app. This will enable us to develop more accurate and reliable algorithms and group-specific models for groups with different sleep patterns (e.g., minority ethnic groups). Data analysis is detailed further below.

Data collection:

Quantitative Data

We will collect data on the percentage of eligible young people at each stage (recruitment, during participation, retention).

The sleep app (Phone Downtime) will collect data passively while participants use the Sleep Solved and/or SHUTi web-based application.

Via REDCap

At recruitment: full name, date of birth, name of school/college, postcode, and contact details. We will also collect parent/carer contact details if the participant is under the age of 16 years.

At baseline, 6-weeks, 6- and 12-months participants will be invited via email to complete:

- sex at birth,
- gender,
- ethnicity,
- Insomnia Severity Index (ISI),
- Revised Children's Anxiety and Depression Scale (RCADS).

If they are over 18 years old at follow up, they will be asked to complete

- the Patient Health Questionnaire (PHQ) and,
- the General Anxiety Disorder Questionnaire (GAD).

We will send participants text and/or email reminders when a survey is required to be completed.

Qualitative Data

All participants who take part will be invited via REDCap to participate in a one-to-one interview via Microsoft Teams or Zoom. We aim to conduct at least 60 in-depth interviews to understand:

- Perceptions,
- Web-based application use,
- The barriers/facilitators that influence engagement,
- The social issues of sleep the web-based application addresses,
- How sleep is reconfigured in a digital-social world.

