The in-depth qualitative interviews (estimated 60 for data saturation of participants at different time points) will explore participant understandings and attitudes towards sleep and how the boundaries/shape of the 'night-world' are influenced through interactions with others. We will explore how dilemmas get managed and moulded in everyday life, how the digital web-based application alters the landscape of sociality and expertise and whether the web-based application(s) had an impact and if that effect is altered by context. Questions will be explored through use of a topic guide, with changes made to questions based on iterative feedback from participants.

Participants who are interviewed may also be invited to keep diaries (audio/web logs, visual/written) to reflect on the behaviour change approaches (e.g., sleep restriction) which can be used as interview prompts. Details regarding how this data will be collected and stored is in Section 8 of the protocol.

5. Analyses

Analyses will be ongoing. Qualitative methodology will be applied to the audio and written data. Specifically, iterative thematic analysis grounded in participant views (concordant and discordant). Quantitative analyses will also be performed in the study. We will use the probable threshold for anxiety and depression of the RCADS at 6-weeks, 6- and 12-month follow up (adjusted for age/sex at birth) and conduct receive operator characteristic (ROC) analyses with appropriate confidence intervals to determine the sensitivity of insomnia screening. We will also compare anxiety and depression scores before and after each step and report whether we have found a signal.

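### The ROC for insomnia screening names only follow-up RCADS waves, all after STEP 1 has begun, so its sensitivity mixes detection with programme effect and existing cases

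*Protocol*

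**What the plan says.** Question 4 in section 3 of the protocol asks: "How effective is the detection of early mental health symptoms using insomnia symptoms". Section 5 answers it with a ROC analysis "to determine the sensitivity of insomnia screening", and fixes the outcome as follows: "We will use the probable threshold for anxiety and depression of the RCADS at 6-weeks, 6- and 12-month follow up". Section 4 (Optimisation and Evaluation) makes the same choice of waves: "Follow up questions on insomnia, anxiety and depression symptoms at 6-weeks, 6- and 12-months will enable us to test detection efficacy".

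Section 4 (Data collection) shows that a baseline pair of measurements exists. The list that includes ISI and RCADS is introduced by "At baseline, 6-weeks, 6- and 12-months participants will be invited via email to complete".

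Section 4 (Materials) describes who receives what. On the first step: "All participants will receive STEP 1 (Sleep Solved) throughout their participation". On the second: "If high levels of sleep disturbance persist at and beyond 6-weeks, the participant will be signposted to STEP 2".

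Section 5 does not say which wave's ISI is the screening result. It does not restrict the ROC to participants below the RCADS threshold at baseline, and it does not account for the steps received.

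**The concern.** A screen is meant to find cases before anything is done about them. Here every wave named for the reference standard comes after the programme has begun. STEP 1 reaches everyone. STEP 2 goes to participants selected on a construct close to the one being evaluated as a screen. Section 2 expects insomnia treatment to lower psychopathology, and question 5 tests for that reduction in the same cohort. A good result on question 5 can therefore change the answer to question 4.

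There is a second mixture. The sample-size text expects most participants with insomnia at enrolment to have mental health symptoms already. A follow-up ROC that keeps them measures largely how well insomnia marks existing cases, whereas question 4 asks about early symptoms. As written, the estimate is neither clean concurrent detection nor clean early detection.

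**Working it through.** **Inputs from the protocol (section 4, Sample size).** 1000 recruited, 20% attrition, 30% with insomnia at enrolment, 75% of those with mental health symptoms. The protocol's counts reproduce:

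- 1000 × (1 − 0.20) = 800
- 800 × 0.30 = 240
- 240 × 0.75 = 180

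**Assumptions.** The protocol gives none of these three quantities:

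- q: proportion with mental health symptoms among those without insomnia, taken as 10%, 20% and 30%
- r: proportion of mental health cases resolved among those with insomnia
- s: the same proportion among those without insomnia

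I treat insomnia symptoms as a positive screen at one cut-off, and mental health symptoms as RCADS caseness.

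**Table at enrolment.** True positives 180; false positives 240 − 180 = 60; false negatives 560q; true negatives 560(1 − q), where 560 = 800 − 240.

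**Sensitivity.** At enrolment: 180 / (180 + 560q). After the programme: 180(1 − r) / [180(1 − r) + 560q(1 − s)].

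| q | Enrolment | r = 10%, s = 0 | r = 30%, s = 0 | r = 30%, s = 15% | r = s = 30% |
|---|---|---|---|---|---|
| 10% | 180/236 = 0.763 | 162/218 = 0.743 | 126/182 = 0.692 | 126/173.6 = 0.726 | 0.763 |
| 20% | 180/292 = 0.616 | 162/274 = 0.591 | 126/238 = 0.529 | 126/221.2 = 0.570 | 0.616 |
| 30% | 180/348 = 0.517 | 162/330 = 0.491 | 126/294 = 0.429 | 126/268.8 = 0.469 | 0.517 |

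With s = 0 the fall is 2.0 to 2.6 points at r = 10% and 7.0 to 8.9 points at r = 30%. With r = 30% and s = 15% it is 3.7 to 4.8 points. With r = s there is none.

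**Comparison with sampling error.** The 95% half-width, 1.96 × √[sens(1 − sens)/cases], is 0.054, 0.056 and 0.053 on 236, 292 and 348 cases. The fall at r = 30%, s = 0 exceeds it; the fall at r = 10% does not.

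**Role of the index wave.** A true positive whose mental health resolves leaves both numerator and denominator of sensitivity, whichever ISI wave is the screen. The other consequences depend on the wave (q = 20%, r = 30%, s = 0; 180 × 0.30 = 54 move):

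- Baseline ISI: the 54 become false positives, and specificity goes from 448/508 = 0.882 to 448/562 = 0.797.
- Same-wave ISI, insomnia and mental health both resolve: the 54 become true negatives, and specificity goes to 502/562 = 0.893.
- Same-wave ISI, only the insomnia resolves: the 54 become false negatives, and sensitivity goes to 126/292 = 0.432.

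**Existing cases.** Of the 240 with insomnia, 180 are already cases at enrolment. Only 60 could show early detection of new caseness, against 504, 448 or 392 below threshold without insomnia (q = 10%, 20%, 30%).

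**The case against.** The strongest defence is that follow-up waves are a deliberate choice. Question 4 concerns early symptoms, and a prospective outcome suits that better than a cross-sectional one. A baseline ROC consists of existing cases and cannot stand alone as the answer. This stands, and it is why the baseline ROC should be added and not substituted. It does not rescue the current text, because a prospective reading needs participants who are below threshold at the start, and section 5 has no such restriction. The exclusion of those already in treatment removes some existing cases, yet the protocol still plans for 180.

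A second defence is that the index wave, the restriction and displays by step are often left to an SAP, and that section 5 does not rule out a baseline ROC. Fair, but the choice of outcome waves is not deferred: the protocol makes it twice, each time without baseline.

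Third, the effect may be small. STEP 2 reaches only those whose disturbance persists, and section 2 reports that about half of iCBT modules are completed on average. Suppose half of the cases persist, half of those engage and 30% of those resolve. Then r = 0.5 × 0.5 × 0.30 = 7.5%, and with s = 0 sensitivity falls to 166.5/222.5 = 0.748, 166.5/278.5 = 0.598 or 166.5/334.5 = 0.498. That is 1.4 to 1.9 points, well within sampling error. These rates are assumptions too and cover the STEP 2 component alone, but they show that a modest distortion is quite possible.

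Finally, the study is an exploratory cohort, no decision rule rests on this ROC, and the baseline data are kept either way. That limits the severity.

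**Conclusion.** The point holds and should be fixed; it is not critical to the study. Followed as written, the sensitivity for question 4 is estimated only after STEP 1 has begun, and at 6 and 12 months also after a step allocated on persisting sleep disturbance. Existing cases are left in. The direction of the distortion rests on one condition: a proportionally larger benefit in young people with insomnia. The insomnia-targeted content and selective STEP 2 make that the design's own expectation, but it is not certain. The sizes are illustrative, because q, r and s are assumed.

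A reader might infer more than the documents support:

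- **That STEP 2 affects all three waves.** It is offered from 6 weeks onward, so the 6-week wave reflects STEP 1 only.
- **That treated participants become false positives and so lower sensitivity.** False positives affect specificity, and this path needs a baseline index that the protocol does not name.
- **That every screen-positive is treated.** The trigger is sleep disturbance, a term the protocol also uses for what the phone app infers, and no ISI cut-off is given.
- **That the fall is 15-17 points.** This needs half of all cases with insomnia to resolve and none of the others (90/146 = 0.616, 90/202 = 0.446, 90/258 = 0.349). Nothing in the protocol supplies that rate.
- **That baseline offers a complete sample of 1000.** Participants are invited by email to complete that survey, so some may not.

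**What to change.** In section 5, and to match in section 4 (Optimisation and Evaluation):

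1. Add a ROC of baseline ISI against baseline RCADS caseness as the estimate of concurrent detection least affected by the steps. The protocol does not state whether the baseline survey precedes Sleep Solved use, so check this in the data and report it. Access to the programme need not be changed.
2. For early detection, analyse baseline ISI against new RCADS caseness at 6 weeks, 6 months and 12 months among participants below threshold at baseline.
3. Label the follow-up results as accuracy under intervention, and show the 6- and 12-month results by STEP 2 entry. That display is descriptive; it does not recover accuracy without the programme.
4. Name the ISI wave that serves as the screening result in each analysis.

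The cost is a change of wording and some extra analysis; both instruments are already collected at every wave. The downside is precision. On the protocol's figures only 60 participants with insomnia would enter the new-onset analysis, so it will have fewer cases and wider confidence intervals than a ROC that keeps existing cases.

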The majority (60-70%) of CYP's mental health problems go undetected and untreated, despite the existence of effective interventions for both management and prevention (1,2). CYP don't seek help because they are either unaware of their symptoms or risk, have concern about stigma, or have limited/no access to mental health services (3,4). Identifying insomnia symptoms is an innovative mechanism to identify young people at risk, and those with early onset mental health problems. Most CYP with mental health problems have symptoms of insomnia (e.g., difficulty getting to sleep, waking at night and finding it hard to go back to sleep, waking frequently or waking early). Insomnia symptoms increase the risk for developing subsequent mental health disorders 2-4-fold. CYP with three insomnia symptoms have a 6-fold increased risk of suicidal ideation, a 10-fold increased risk of a suicide attempt and an increased risk of completing suicide (5,6).

Addressing insomnia reduces mental health problems and the risk of suicide. Automated internet-based cognitive behavioural therapy (iCBT) for adults reduces insomnia and depression with medium effect sizes (7). Most studies have been conducted in those with chronic insomnia, but early identification and support for "acute" (i.e., less than 3 months) insomnia symptoms may be more effective (8). In CYP, iCBT for insomnia is effective in reducing insomnia symptoms mediating a reduction in psychopathology and an improvement in wellbeing. However, studies to date have been relatively small feasibility studies (9–11).

Digital interventions delivering automated iCBT are effective for CYP with anxiety/depression with small to medium effect sizes (12). Automated iCBT has several advantages including: delivering support for CYP at scale; delivering support asynchronously so CYP can complete modules privately without fear of stigma; being able to target support to those with symptoms; self-completion is empowering (13). However, automated iCBT for insomnia has sub-optimal adherence. On average only ~50% of modules are completed (7,9–11). Brief, single-session approaches are effective for insomnia in adults and are likely to improve engagement with those from deprived backgrounds or those with mild cognitive impairments (14,15). Therefore, using smartphones to detect insomnia symptoms and offer intervention provides a novel mechanism to improve insomnia and mental health problems.

Development and Adaptation

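### The ROC for research question 4 omits baseline, and at 6 and 12 months the insomnia being tested as a screen has influenced who was offered STEP 2

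*Protocol*

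**What the plan says.** Research question 4 (Protocol, 3. Aims & Objectives) asks: "How effective is the detection of early mental health symptoms using insomnia symptoms". Section 5 (Analyses) fixes the reference standard: "We will use the probable threshold for anxiety and depression of the RCADS at 6-weeks, 6- and 12-month follow up". The method is ROC "analyses with appropriate confidence intervals to determine the sensitivity of insomnia screening". Section 4, Optimisation and Evaluation, names the same waves: "Follow up questions on insomnia, anxiety and depression symptoms at 6-weeks, 6- and 12-months will enable us to test detection efficacy".

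The ISI and RCADS are also collected together before follow-up starts (section 4, Data collection): "At baseline, 6-weeks, 6- and 12-months participants will be invited via email to complete" both scales. That baseline pair is not named for the ROC. The protocol does not say which ISI wave is the index test.

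On treatment, section 4, Materials, gives STEP 1 to everyone and then states: "If high levels of sleep disturbance persist at and beyond 6-weeks, the participant will be signposted to STEP 2". The Background (Justification) says of young people that "iCBT for insomnia is effective in reducing insomnia symptoms mediating a reduction in psychopathology". Research question 5 sets out to test whether mental health symptoms fall after STEP 1 and STEP 2. Section 5 does not mention STEP 2 exposure in connection with the ROC.

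**The concern.** A screening accuracy estimate assumes that nothing driven by the index condition changes the reference outcome between test and verification. Here persistent sleep disturbance leads to an offer of insomnia treatment, and that treatment is expected to lower anxiety and depression. A young person correctly flagged by an early ISI, whose symptoms then resolve under STEP 2, enters the 6- or 12-month table as a false positive.

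The 6- and 12-month answer to research question 4 therefore depends in part on the answer to research question 5: a more effective programme tends to make the screen look worse. The one ISI and RCADS pair taken before any step is left out. A reader of the later ROCs could undervalue insomnia screening, or could not tell weak detection from successful treatment.

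**Working it through.** **Inputs from the protocol (section 4, Sample size).** 1000 × (1 − 0.20) = 800 with data; 800 × 0.30 = 240 with insomnia symptoms; 240 × 0.75 = 180 of these with mental health symptoms. The stated 800, 240 and 180 reproduce exactly. That leaves 240 − 180 = 60 false positives and 800 − 240 = 560 screen-negatives. These are enrolment figures and serve here only as an illustrative untreated table.

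**Assumed inputs, not given in the document.** q is the share of the 560 screen-negatives with mental health symptoms, taken as 10–30%. e is the net share of the 180 moved below the RCADS threshold by STEP 2. It is the product of persistence s, uptake u and resolution r.

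**Formulas for an earlier ISI as index test, with STEP 2 alone acting.**

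Sensitivity = 180(1 − e) / [180(1 − e) + 560q]

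Specificity = 560(1 − q) / [560(1 − q) + 60 + 180e]

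At q = 20% (112 false negatives, 448 true negatives):

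| e | True positives | False positives | Sensitivity | Specificity | Mean of the two |
|---|---|---|---|---|---|
| 0 | 180 | 60 | 0.616 | 0.882 | 0.749 |
| 10% | 162 | 78 | 0.591 | 0.852 | 0.721 |
| 20% | 144 | 96 | 0.562 | 0.824 | 0.693 |
| 30% | 126 | 114 | 0.529 | 0.797 | 0.663 |

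From e = 0 to e = 30%, sensitivity goes from 0.763 to 0.692 at q = 10%, and from 0.517 to 0.429 at q = 30%. The direction is the same throughout; the largest fall is about 9 points.

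**Allowing for persistence and uptake (q = 20%).** For the low end of s, I borrow 28%, the complement of the protocol's 72% recovery for new acute insomnia. For u, I assume 50%, with the protocol's figure of about half of modules completed as a loose guide.
- Low: e = 0.28 × 0.5 × 0.2 = 0.028; sensitivity = 174.96 / 286.96 = 0.610, a fall of 0.7 points.
- Middle: e = 1 × 0.5 × 0.4 = 0.20; sensitivity = 144 / 256 = 0.562, a fall of 5.4 points.
- High: e = 1 × 1 × 0.3 = 0.30; sensitivity = 126 / 238 = 0.529, a fall of 8.7 points.

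For scale, the 95% half-width for 0.616 on 180 + 112 = 292 cases is 1.96 × √(0.616 × 0.384 / 292) = 0.056.

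**If screen-negatives are also treated.** With a share f of the 112 cleared through STEP 3, sensitivity = 180(1 − e) / [180(1 − e) + 112(1 − f)]. At e = 20% and f = 10% this is 144 / (144 + 100.8) = 0.588, against 0.562 without STEP 3. At f = e it is back at 180 / 292 = 0.616. Specificity does not recover in the same way: at e = f = 20% it is 470.4 / (470.4 + 96) = 0.831, against 0.882 untreated.

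**Choice of index wave.** A latent-normal simulation used 1,000,000 subjects and 30% cut-offs on both scales. Same-visit correlation was assumed to be 0.6, and ISI correlations across waves 0.70–0.80. STEP 2 was given to those above the cut-off at both baseline and 6 weeks, with an assumed effect of 0.5 SD on both scales:

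| Index ISI | Sensitivity | Specificity | AUC |
|---|---|---|---|
| Baseline | 0.483 to 0.390 | 0.779 to 0.732 | 0.698 to 0.631 |
| 6-week | 0.507 to 0.418 | 0.790 to 0.742 | 0.723 to 0.657 |
| Same-visit | 0.577 to 0.484 | 0.819 to 0.836 | 0.787 to 0.755 |

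With a same-visit ISI, specificity rose here. It fell to 0.781 when only the mental health scale responded. Its direction thus depends on how the two scales respond.

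**The case against.** The strongest case against has four parts.

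- **The trigger is narrow.** STEP 2 needs disturbance that persists to 6 weeks, and it is signposted, not assigned. A reader might infer that one positive baseline ISI leads to treatment; the Materials text does not say that. With low persistence and partial uptake, the fall in sensitivity can be smaller than the 0.056 half-width. This stands as to size. It does not remove the problem, because a confidence interval does not cover systematic error.
- **The 6-week ROC is already planned.** It precedes any STEP 2 effect, so the claim that all of research question 4 is biased by STEP 2 would be wrong. This stands. The 6-week result is still not untreated, since everyone has STEP 1.
- **The direction is not guaranteed.** Section 4 (Overarching Design) opens STEP 3 to anyone seeking further mental health advice, while section 7 (Benefits to participants) describes it after SHUTi. The two passages need to be reconciled. On the first, symptomatic screen-negatives may also improve, which supports sensitivity. The same-visit reading of the index test is also open. Both stand as limits on any statement that every accuracy measure is biased downwards.
- **No decision rule hangs on the ROC, and baseline data are collected anyway.** This stands and lowers the severity. It also means that correction costs little.

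A further tempting step is to quote a fall in positive predictive value from the 75% at enrolment (180/240) as a forecast for 6 or 12 months. The document does not support this: natural remission and new onset would also move those cells without any treatment.

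**Conclusion.** The point holds in a limited form. By naming only follow-up RCADS, the plan omits the one pre-intervention ISI and RCADS pair, and it includes two waves at which the screened condition has influenced who was offered treatment. If STEP 2 works and the index test is the baseline or 6-week ISI, sensitivity, specificity and AUC at 6 and 12 months tend to be understated. If STEP 2 has no effect on the RCADS, this bias is zero.

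The mechanism follows from the document; the size does not. A fall in sensitivity of under 1 to about 9 points rests on assumed symptom prevalence among screen-negatives (10–30%) and assumed net clearance among screen-positive cases (about 3–30%), with no STEP 3 effect. Severity is moderate: the conclusion on research question 4 is at risk, but the data needed to protect it are already being collected.

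**What to change.** In section 5:

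1. Add the ROC of baseline ISI against baseline RCADS (up to n = 1000, before any step) as the untreated, cross-sectional accuracy estimate.
2. State which ISI wave is the index test for each follow-up ROC.
3. Make the 6-week RCADS the main prospective outcome, noting that STEP 1 has been available to all by then.
4. Keep the 6- and 12-month ROCs, label them accuracy under stepped care, report STEP 2 uptake beside them, and do not base the conclusion on research question 4 on them.

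Do not split the ROC by whether STEP 2 was offered. The offer depends on persistent sleep disturbance, so the split conditions on the index test and restricts its range within each group.

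The cost is a few sentences and one more analysis of data already collected. The downside is a headline prospective horizon of 6 weeks instead of 12 months; the baseline ROC describes concurrent detection and does not replace prediction.
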